**Aim(s) of the Research**

1- To evaluate the presence of SF3B1-K700E mutation in acute lymphoblastic leukemia and chronic lymphocytic leukemia using PCR technique

ARMS PCR technique will be used to detect the presence of SF3B1-MUTATION in acute lymphoblastic leukemia and chronic lymphocytic leukemia

2-To determine the effect of presence of SF3B1-K700E mutation with other laboratory findings.

determine if the presence of SF3B1-mutation can affect the clinical data as severity of disease or organomegaly and laboratory data as count of white blood cells and platelet and hemoglobin level using automated cbc analyser and bone marrow of the patients (cellularity and count of blast cells) and result of flow cytometry

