Mutated *SF3B1* gives rise to a protein with a neomorphic activity linked to several mechanisms involved in RNA processing. About half of aberrantly spliced mRNAs are characterized by the presence of premature stop codons, resulting in nonsense-mediated RNA decay and downregulation of the protein expression. Although the wild-type allele is still able to be expressed, the amount of protein produced is unable to compensate for the mutant allele. Another possibility is the translation of new proteins that lack the correct biological function and/or that acquire aberrant functions

A study has shown Hotspot K700E and non-K700E *SF3B1mut* MDS show distinct clinical and mutational profiles in MDS, with K700E showing significantly better Overall survival than non-K700E and *SF3B1wt*. Only the absence of the *SF3B1mut* K700E mutation independently predicted worse Overall survival in MDS. Hence, identification of the *SF3B1* mutation type is important for risk stratification.

In the study by Wang and colleges, somatic mutations of *SF3B1* were found in approximately 15% of patients, making this the second most frequently mutated gene in CLL.

In a cohort of 537 unselected CLL cases, *SF3B1* mutations were present in (8.9%) of cases , The residues surrounding Lys700 were the most frequently mutated (48%).

Quesada and colleges in 2012 studied 279 untreated patients with CLL and found *SF3B1* mutations in 27 (10%) [15]. the most frequent mutation was K700E, occurring in almost half of the cases, No *SF3B1* mutation was detected in 156 patients with non-Hodgkin lymphoma [15]. CLL patients with mutations in *SF3B1* had more aggressive disease and shorter overall survival than patients without these mutations.

Another study provided evidence that the *SF3B1* inhibitor H3B-8800 displays therapeutic effects in mouse models of CLL, particularly when used on CLL cells harbouring *SF3B1* mutations.

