#### **-Data management and analysis:**

Analysis of data by SPSS program. Data will be expressed as mean $\pm$  SD, number and percentage. Correlation between categorical variables will be performed in 2x2 contingency tables using Fisher's exact test. Comparison between metric variables will be done using Mann-Whitney test and Wilcoxon signed ranks test. Exact p value (2-sided) will be calculated and a value  $\leq 0.05$  is considered statistically significant.

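### Does Aim 2 promise more than one or two expected K700E carriers among the CLL patients can support?

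*Protocol*

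**What the plan says.** Under Aim(s) of the Research, Aim 2 is stated as "To determine the effect of presence of SF3B1-K700E mutation with other laboratory findings". The explanatory text below it says the study will "determine if the presence of SF3B1-mutation can affect the clinical data as severity of disease or organomegaly", and goes on to blood counts, marrow findings and flow cytometry.

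Data management and analysis names Fisher's exact test for categorical variables and states "Comparison between metric variables will be done using Mann-Whitney test". It adds "Exact p value (2-sided) will be calculated", with 0.05 as the threshold.

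Study subjects fixes 28 patients with ALL, 28 with CLL and 28 controls. Sample Size Calculation rests on a one-way ANOVA across these three groups and says nothing about carriers against non-carriers.

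The Introduction supplies rates for CLL only. In one cohort SF3B1 "mutations were present in (8.9%) of cases", with 48% of them around Lys700. In a second, 27 of 279 patients were mutated and "the most frequent mutation was K700E, occurring in almost half of the cases". In a third, mutations "were found in approximately 15% of patients". It gives no rate for ALL.

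**The concern.** Aim 2 is worded as a question that will be settled, and the protocol attaches significance tests to it. Yet the protocol's own background suggests that the carrier group within CLL may be empty or hold a single patient. With no carrier there is nothing to compare, and with one carrier some of the named tests cannot reach the threshold whatever the data show. A reader of the final report might then take a missing or non-significant test as evidence that the mutation has no effect.

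Two further features add to the doubt. The aim names K700E in its heading but SF3B1 mutation in general in its explanation, which could change who counts as a carrier. It also does not say whether carriers are compared within each disease or across all leukemia patients. If ALL and CLL were put together, a difference in white cell or blast count could reflect the diagnosis rather than the mutation, because the named tests have no term for disease.

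**Working it through.** **1. The plan's own figure.** One-way ANOVA, three groups, f = 0.4, alpha 0.05. With 28 per group, the noncentrality is 84 × 0.4² = 13.44 on 2 and 81 degrees of freedom, and power is 0.907. With 27 per group it is 0.895. The stated total of 84 is therefore reproduced for 90% power. It concerns the three-group comparison only.

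**2. Expected K700E carriers among 28 CLL patients** (rate × K700E share × 28, inputs from the Introduction):

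| Source | K700E rate p | Expected, 28p | P(none) = (1−p)^28 | P(none or one) |
|---|---|---|---|---|
| 8.9% × 48% | 4.3% | 1.2 | 29% | 66% |
| 27/279 × one half | 4.8% | 1.4 | 25% | 60% |
| 15% × 48% | 7.2% | 2.0 | 12% | 39% |

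The last row borrows the 48% share from the first cohort, because the 15% study has none stated; one half would give 2.1. The 48% refers to residues around Lys700, so strict K700E may be rarer. If any SF3B1 mutation counted, the expected number would be 28 × 0.089 = 2.5 to 28 × 0.15 = 4.2.

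**3. Smallest attainable p-values.** For the two-sided exact Mann-Whitney test with m carriers among N patients, the minimum is 2/C(N, m).
- N = 28, m = 1: 2/28 = 0.071, so 0.05 is out of reach.
- N = 28, m = 2: 2/378 = 0.005.
- N = 56, m = 1: 2/56 = 0.036, so 0.05 is within reach.

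Fisher's test with one carrier of 28 reaches 1/28 = 0.036 if that carrier alone has the finding. With two carriers who both have it, four of the 26 non-carriers may also have it: C(6,2)/C(28,2) = 15/378 = 0.040. A fifth gives 21/378 = 0.056.

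**4. Precision with two carriers.** The 95% half-width in SD units is t × √(1/m + 1/(N−m)). For 2 against 26 it is 1.51 SD; for 2 against 54 it is 1.44 SD.

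**5. Power for an assumed shift of 1 SD** (the protocol states no effect size for Aim 2; simulated with normal data). Within CLL it is 0% with one carrier and 23% with two. Averaged over the random number of carriers, it is about 9% to 17%. If ALL had the same K700E rate as CLL, which is an assumption, the comparison over all 56 patients would have about 27% to 41%.

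**The case for a change.** The strongest case for a change is that the one-carrier limit is arithmetic and not merely low power. It needs no assumed effect size, and on two of the three cited rates the CLL group is more likely than not to have no carrier or one. The wording of the aim stands in the protocol, and an analysis plan cannot rewrite it. Calling the aim exploratory would cost only words.

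The carrier counts stand, and so does the warning that a non-significant result would say little. The step from there to a fault in the plan does not. The limit applies to Mann-Whitney within CLL, an analysis the protocol does not single out. It does not apply to Fisher's test, or to one carrier among all 56 patients. The total number of carriers for Aim 2 is unknown without an ALL rate. Nothing in the protocol says that non-significance will be read as absence of effect.

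The change from K700E to SF3B1 mutation also appears in Aim 1, whose heading names K700E before its explanation uses the general term. It reads as shorthand for the mutation just named. Confounding by disease would arise only under a combined analysis without stratification, which the protocol does not state.

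**Conclusion.** No change is called for. Comparisons of carriers with non-carriers within CLL will be very imprecise: about 1.2 to 2.0 carriers expected, and an interval of about ±1.5 SD with two. This assumes that the CLL rates in the Introduction apply to the recruited patients, and it says nothing about ALL.

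This is a limit of a secondary aim for which the protocol claims no power, so no stated figure is missed, and the tests chosen remain valid in small samples. A rule for none or one carrier, analysis by disease and reporting of confidence intervals are details commonly left to an analysis plan; only the protocol was available here, so their absence from it is not a fault. A softer verb in Aim 2 would be a matter of taste and would alter neither the data collected nor the tests.

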#### **-Data management and analysis:**

Analysis of data by SPSS program. Data will be expressed as mean $\pm$  SD, number and percentage. Correlation between categorical variables will be performed in 2x2 contingency tables using Fisher's exact test. Comparison between metric variables will be done using Mann-Whitney test and Wilcoxon signed ranks test. Exact p value (2-sided) will be calculated and a value  $\leq 0.05$  is considered statistically significant.

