**3- Study subjects:**

Study will be conducted on peripheral blood samples of 28 acute lymphoblastic leukemia patients, 28 chronic lymphocytic leukemia patients and 28 control.

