**c. Sample Size Calculation:**

Based on determining the main outcome variable, the estimated minimum required sample size is 84 patients (28 patient in each group)

The sample was calculated using G\*power software 3.1.9.2., based on the following assumptions:

Main outcome variable is the difference between mean value of Sf3b1 mutation between the groups

1- patients with chronic lymphocytic leukemia

2- patients with acute lymphoblastic leukemia

3- control group free from the disease

Based on clinical experience we expected to find large effect size difference between 3 groups

Main statistical test is one-way Anova to detect the difference between the 3 groups.

Alpha = 0.05

Power = 0.90

Effect size = 0.4

**4 –Study tools (in detail, e.g., lab methods, instruments, steps, chemicals, ...):**

- Medical history (age, sex, complaint of the patients)

- Clinical examination emphasizing on hepatomegaly, splenomegaly and lymphadenopathy.

- Imaging: ultrasound.

- Laboratory investigation: Complete blood count (CBC)

  - Reticulocyte count and Peripheral blood film.

  - Liver and kidney function test

  - Prothrombin time, concentration and INR.

  - Bone marrow examination.

Specific laboratory investigation: ARMS PCR for SF3B1 mutation.

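### Metric variables are summarised by mean and SD but compared by ranks, so the difference printed for Aim 2 is not the quantity tested (minor)

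*Protocol*

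**What the plan says.** All the relevant text is in the protocol.

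- **Summary.** Under Data management and analysis: "Data will be expressed as mean" with SD, plus numbers and percentages. No median, quartiles or rank-based estimate is named.
- **Test.** The same section says "Comparison between metric variables will be done using Mann-Whitney test and Wilcoxon signed ranks test", and adds "Exact p value (2-sided) will be calculated".
- **Where it applies.** The second aim, under Aim(s) of the Research, relates mutation status to "laboratory data as count of white blood cells and platelet and hemoglobin level", and also to the marrow blast count.
- **Group sizes.** Study subjects gives "28 acute lymphoblastic leukemia patients, 28 chronic lymphocytic leukemia patients and 28 control".

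The protocol states no expected number of carriers and does not describe how any laboratory variable is distributed.

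**The concern.** Choosing exact rank tests implies that normality is not being relied on. Mean and SD are the summaries most sensitive to skew and to single extreme values. Printed side by side, they answer different questions. The mean difference can be driven by one patient with a very high count. The Mann-Whitney test asks whether carriers tend to rank above or below non-carriers.

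With large groups the mismatch would be mostly cosmetic. Here the carrier group will be very small, so most Aim 2 comparisons will probably be non-significant and readers will rely on the descriptive difference. That is where a mean pulled by an outlier misleads about the size, and sometimes the direction, of what was seen. An SD from two values only rescales their difference, and from one value it does not exist.

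**Working it through.** **1. The plan's own figure.** For one-way ANOVA with three groups, alpha 0.05 and "Effect size = 0.4" (Cohen's f), noncentrality is f²·N with 2 and N − 3 degrees of freedom. N = 84 gives 0.16 × 84 = 13.44 and power 0.907; N = 81 gives 0.895. So 84 (28 per group) is the smallest balanced total reaching 0.90. The figure reproduces and does not depend on how data are summarised.

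**2. How many carriers.** The Introduction cites any-SF3B1 rates in CLL of 8.9%, 10% and about 15%, with 48% to almost half of mutations at or around codon 700. I assume the comparison is made within the 28 CLL patients; no rate is given for ALL.

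| Definition | Expected carriers = 28 × rate |
|---|---|
| Any SF3B1 mutation | 28 × 0.089 = 2.5; 28 × 0.10 = 2.8; 28 × 0.15 = 4.2 |
| K700E (the mutation in the aims) | from 28 × 0.089 × 0.48 = 1.2 to 28 × 0.15 × 0.50 = 2.1 |

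From the binomial distribution for K700E: zero or one carrier, 37 to 66%; exactly one, 26 to 37%; two or three, 31 to 48%.

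**3. Can summary and test disagree?** A constructed example with 3 carriers (56, 57, 58) against 25 non-carriers (6, 8, 9, 11, 12, 14, 15, 17, 18, 20, 22, 24, 26, 28, 30, 33, 36, 39, 42, 46, 50, 55, 70, 320, 600):

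- Means: 171/3 = 57.0 against 1551/25 = 62.0, so carriers look lower by 5.0.
- Medians: 57 against 26, so carriers look higher.
- Exact two-sided Mann-Whitney p = 0.032, with carriers ranking higher.
- Hodges-Lehmann difference (median of the 75 pairwise differences): +31, in agreement with the test.

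**4. How often.** Simulation of 40,000 log-normal samples of 28 per setting, counting samples where the mean difference and the rank sum (against its null mean) point opposite ways. The log-SD is an assumption, so a range is shown.

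| log-SD | 2–3 carriers, no effect | 2–3 carriers, doubled median |
|---|---|---|
| 0.5 | 9–12% | 1–2% |
| 0.8 | 13–17% | about 8% |
| 1.0 | 16–19% | 13% |
| 1.5 | 21–25% | 23–24% |

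**5. How often with p ≤ 0.05.** As a share of significant results with two or three carriers, reversal is about 0% at log-SD up to 1.0, at most 1.4% at 1.5 and at most 1.9% at 2.0. These maxima occur with no true effect, where only about 4 to 5% of samples are significant, so a significant reversal then occurs in at most about 0.05 × 0.019 = 0.1% of studies.

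**6. What a rank-based interval can deliver.** The widest exact Hodges-Lehmann interval has confidence 1 − 2/C(28, m). With m = 1: 1 − 2/28 = 92.9%, so no 95% interval exists. With m = 2: 1 − 2/378 = 99.5%, so a 95% interval is available.

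**The case against.** Five objections deserve an answer.

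- **The p value is two-sided and has no direction.** A reader might infer that the printed difference will often contradict a significant p value. Step 5 does not support that: nearly all reversals sit among non-significant results. This objection stands and limits the point to description.
- **Skew is not in the documents.** Correct. It is assumed for white cell and blast counts. There is no equal argument for haemoglobin, and the size of the effect falls quickly as the assumed skew falls.
- **Two or three carriers is a scenario, not a plan figure.** Also correct. For K700E, zero or one carrier is more likely than not at the 8.9 and 10% rates. With none there is no comparison. With one, the smallest exact two-sided p is 2/28 = 0.071 whatever summary is printed. Changing the summary does not cure the scarcity of carriers.
- **Mean minus SD below zero.** Under the assumed skew this occurs in most samples of 28 (about 57 to 97% at log-SD 1.0 to 1.5, but 20% at 0.8). A reader might infer that the SD asserts impossible counts. It does not; it describes spread, and such a value only signals skew.
- **Descriptive formats often belong in an analysis plan.** One may exist, and the protocol does not forbid medians. But it does not leave the matter open: it names a summary and a test that do not match. Quartiles of two or three values are no better than an SD, which is why individual values are the right display there.

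**Conclusion.** The point holds as a minor reporting weakness. The protocol pairs a moment-based summary with rank-based tests, so Aim 2's printed difference is not what is tested. Under assumed log-normal counts with log-SD 1.0 to 1.5 and two or three carriers among 28, the two point opposite ways in about 13 to 25% of samples, with fewer than 2% of significant results affected. That range rests on the assumed skew, on a comparison within the CLL group, and on a carrier number that the cited prevalences make plausible but not certain. The validity of the Mann-Whitney test, its p values and the total of 84 is not in question.

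**What to change.** In the protocol's Data management and analysis section:

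1. Report median and quartiles for skewed metric variables such as white cell and blast counts. Mean and SD may stay for roughly symmetric ones such as haemoglobin.
2. Beside each Mann-Whitney p, give the Hodges-Lehmann difference with its 95% confidence interval where carrier numbers allow one.
3. When there are fewer than five carriers, list their individual values instead of an SD or quartiles.

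The cost is a sentence or two of text and slightly longer tables; the data and the tests stay the same. With a single carrier no 95% interval exists, and the report should say so. The change should be made before the data are analysed, so that the choice of summary cannot follow the results.

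### The only route for categorical findings is a 2x2 Fisher test, which with the one or two carriers to be expected in CLL often cannot reach 0.05; recording organ size as a measurement is a cheap improvement

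*Protocol*

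**What the plan says.** The protocol's data management and analysis section has two routes. For categorical variables: "Correlation between categorical variables will be performed in 2x2 contingency tables using" Fisher's exact test. For metric variables: Mann-Whitney and Wilcoxon signed ranks tests. P values are exact and two-sided, with 0.05 as the threshold.

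Aim 2 asks whether the mutation can "affect the clinical data as severity of disease or organomegaly", and then turns to blood counts, marrow cellularity and blast count, and flow cytometry. The study tools list "Clinical examination emphasizing on hepatomegaly, splenomegaly and lymphadenopathy" and, as a separate item, "Imaging: ultrasound". It does not say what is recorded from the ultrasound, or whether organ enlargement is kept as a measurement, a grade or a yes/no item.

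The study subjects are "28 acute lymphoblastic leukemia patients, 28 chronic lymphocytic leukemia patients and 28 control", and patients of any age are eligible. The expected number of carriers is not stated.

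**The concern.** A 2x2 table accepts only two levels. If enlargement of liver, spleen or nodes is noted as present or absent, it goes straight into that table. Any severity or cellularity variable with three or more grades must first be collapsed. Both steps discard information, and the loss is greatest when one of the compared groups holds only one or two people.

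With so few carriers, Fisher's test has very few possible outcomes. For findings of middling frequency, even the most extreme outcome does not reach 0.05. A comparison under Aim 2 could then be non-significant before any data are seen. The plan already contains an imaging method that can yield organ size and a test that would use it. If the sizes are not written down during the study, they may not be recoverable later.

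**Working it through.** **The plan's own figure.** The sample size section states "Main statistical test is one-way Anova to detect the difference between the 3 groups" and "Effect size = 0.4", with alpha 0.05 and power 0.90. With the noncentral F distribution (noncentrality 0.4² × N, degrees of freedom 2 and N − 3), power is 0.895 at N = 81 and 0.907 at N = 84. The stated 84 reproduces. It sizes a comparison of means across three groups and says nothing about carriers against non-carriers, which is what matters here.

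**Expected carriers in CLL.** The Introduction gives SF3B1 rates in CLL of 8.9%, 10% and about 15%. It puts about half of the mutations at K700E (48% at residues around Lys700 in one cohort, almost half in another). K700E is the mutation named in the aims.
- Low: 28 × 0.089 × 0.48 = 1.2
- Middle: 28 × 0.10 × 0.50 = 1.4
- High: 28 × 0.15 × 0.50 = 2.1

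Binomial probabilities at the low and high rates: 0 or 1 carrier, 66% and 37%; at least 2 carriers, 34% and 63%; at least 3 carriers, 12% and 35%. The protocol gives no SF3B1 rate for ALL, so no carrier number can be derived there.

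**Smallest possible Fisher p, 2 carriers of 28.** There are C(28,2) = 378 ways to place the carriers. If m patients have the finding and m is below 14, the most extreme table has both carriers positive, and p = C(m,2)/378:
- m = 6: 15/378 = 0.040
- m = 7: 21/378 = 0.056
- m = 13: 78/378 = 0.206
- m = 14: both tails count, 2 × 91/378 = 0.48

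Above 14 the values mirror these, with both carriers negative: m = 21 gives 0.056 and m = 22 gives 0.040. So 0.05 is out of reach for m = 7 to 21 (25 to 75%) and within reach for m = 2 to 6 and 22 to 26.

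**Other carrier counts among 28.**
- 1 carrier: out of reach for m = 2 to 26.
- 3 carriers, C(28,3) = 3276: m = 10 gives 120/3276 = 0.037 and m = 11 gives 165/3276 = 0.0504, so out of reach for m = 11 to 17.
- 4 carriers: in the middle of the range, only m = 14 is out of reach.

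Pooling both leukemias (56 patients, 2 carriers, C(56,2) = 1540): m = 12 gives 66/1540 = 0.043 and m = 13 gives 78/1540 = 0.051, so out of reach for m = 13 to 43.

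**Measured value, exact Mann-Whitney.** The smallest two-sided p without ties is 2/C(28, carriers): 2/378 = 0.0053 with 2 carriers, but 2/28 = 0.071 with 1.

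**Grades left uncollapsed, 2 carriers.** The smallest exact rank p is 15/378 = 0.040 for a 14/8/6 split and 21/378 = 0.056 for 14/7/7. These equal the 2x2 result when the top grade is set against the rest. Cutting either split at 14 against 14 gives 0.48. The gain lies in not having to choose a cut.

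**Power (simulation, normal data).** The shift is an assumption, as the protocol gives none. With 2 carriers, the rank test has about 9%, 23% and 45% power at shifts of 0.5, 1 and 1.5 SD. At 1.5 SD, Fisher after dichotomising has 0% (cut at the non-carrier median) to about 5% (cut at the 70th percentile). With 3 carriers at 1.5 SD, the figures are about 57% for the rank test against 2% and 30%.

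**The case against.** The strongest reply is that the protocol never says organomegaly is kept as yes/no, nor that severity or cellularity is graded. A span in centimetres would already fall under the metric rule and go to Mann-Whitney, and the recording format may be left to another document. This stands as far as it goes: forced dichotomisation of organ size is not in the text. What the text does fix is that anything categorical goes to a 2x2 table, and it names organ enlargement only as a clinical finding. The blood counts in Aim 2 are unaffected.

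Three further points also stand. Two carriers is the top of the derived range, and with 0 or 1 carrier in a group of 28 (37 to 66% likely in CLL) the rank test cannot reach 0.05 either. Rank-test power is low unless the shift is very large. The gain for coarse grades is small.

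A reader might infer that significance is impossible for every common finding. The arithmetic does not support that: at 22 to 26 of 28 patients, 2 carriers can give p of 0.040 or less if both lack the finding. A reader might also infer that the authors would report a null result as no relation. The protocol does not say so.

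**Conclusion.** The point holds in limited form. The 2x2-only rule for categorical variables is a poor match for Aim 2 when carriers are this scarce. With 2 carriers among 28 CLL patients, no data could give significance for a finding present in 25 to 75% of them; with 3 carriers the same is true for 11 to 17 of 28. A measured value tested by rank can reach 0.005 with 2 carriers.

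This rests on the Introduction's rates applying to these patients, on testing within a group of 28, and on organ enlargement being recorded as present or absent, which is the natural reading of the clinical examination item but is not stated. The main problem is the small number of carriers; dichotomising makes it worse. The change is a cheap improvement to a secondary aim, not the repair of an error that invalidates the study.

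**What to change.** - State that liver and spleen size are recorded as measurements from the planned ultrasound, and compare carriers with non-carriers by the exact Mann-Whitney test already in the plan. Use centimetres in CLL. In ALL, express size relative to the normal value for age or body size, because all ages are eligible and raw span would mix growth with mutation status.
- Analyse any variable with more than two ordered levels uncollapsed, with an exact rank test.
- Keep the 2x2 Fisher test for truly binary items.
- Report the number of carriers with each comparison, and state that a non-significant result is not evidence of no relation.

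The cost is a few recorded numbers per patient, an age or size reference in ALL, and two or three sentences of analysis text. It should be settled before data collection.
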